A Randomized, Double-Blind, Placebo-Control Pilot Trial of Xuanfei Baidu Granules (XFBD), a Traditional Chinese Medicine (TCM), in Persons with COVID-19

Short name: XFBD001

Protocol Version 1.2

Protocol Date: 06/22/2021

University of Southern California

Protocol Chairs:

[name] (Medicine, Biological Sciences and Engineering)

[name] (Preventive Medicine)

[name] (Medicine) Medical Monitor

[name] (Preventive Medicine)

Pharmacist:

[name]

Biostatistician:

[name].

GLOSSARY OF PROTOCOL-SPECIFIC TERMS

AE	adverse event
ARDS	acute respiratory distress syndrome
CFR	Code of Federal Regulations
CI	Confidence Interval
CLIA	Clinical Laboratory Improvement Amendments
COPD	Chronic obstructive pulmonary disease
COVID-19	Coronavirus Disease 2019
CVD	cardiovascular disease
DRESS	drug reaction with eosinophilia and systemic symptoms
DSMB	Data and Safety Monitoring Board
EC	Ethics Committee
eCRF	electronic Case Report Form
FDA	Food and Drug Administration
EKG	electrocardiogram
GCP	Good Clinical Practice
GI	Gastrointestinal
HTN	hypertension
ICU	Intensive care unit
ICF	informed consent form
IND	Investigational New Drug Application
IRB	Institutional Review Board
IV	intravenous
MERS	Middle East Respiratory Syndrome
NIAID	National Institute of Allergy and Infectious Diseases
NIH	National Institutes of Health
OHRP	Office for Human Research Protections
PHI	Protected Health Information
PI	Principal Investigator
SAE	Serious Adverse Event
SAP	Statistical Analysis Plan
SARS-CoV-2	Severe Acute Respiratory Syndrome coronavirus 2
TCM	Traditional Chinese Medicine
XFBD	Xuanfei Baidu Granules
WHO	World Health Organization

SCHEMA

XFBD001

A Randomized Double-Blind Placebo-Control Pilot Trial of Xuanfei Baidu Granules (XFBD), a Traditional Chinese Medicine (TCM), in Persons with COVID-19

DESIGN*Pilot*

This is a randomized double-blind placebo-control pilot trial to document safety and efficacy endpoint assessments and to determine the feasibility of community recruitment and enrollment of symptomatic adult outpatients with COVID-19.

DURATION

12 weeks. Treatment will be for 14 days with 10 weeks of follow-up.

SAMPLE SIZE*Pilot*

60 patients who start study treatment; approximately 30 participants in each of the two treatment arms (A and B). Participants who are randomized and who do not start study treatment will be replaced

POPULATION

Symptomatic, outpatient, adults (≥ 18 years) with SARS-CoV-2 infection

STRATIFICATION

Stratification will be by “high” versus “low” risk of progression to severe COVID-19 disease, where “high risk” is defined as a person age ≥ 60 years or having one of several specified comorbidities.

REGIMEN

Participants will be randomized 1:1 individuals. Participants will receive either XFBD (10 g orally twice a day) for 14 days (Arm A) or a placebo twice a day for 14 days (Arm B).

1. HYPOTHESIS AND STUDY OBJECTIVES

1.1. *Hypothesis*

- 1.1.1. Xuanfei Baidiu granules (XFBD) will prevent hospitalization and death in persons with symptomatic SARS-CoV-2 infection.

1.2. *Primary Objective*

- 1.2.1. To document the feasibility of recruitment through community setting by assessment of the number of positive cases identified per week.
- 1.2.2. To document the proportion of patients who agree to participate as measured by enrollment and randomization.
- 1.2.3. To document the treatment emergent side effects and safety profile of the XFBD and placebo.
- 1.2.4. To document the rate of hospitalization or death within 42 days of enrollment in the XFBD and placebo treated groups.

1.3. *Secondary Objectives*

- 1.3.1. To document the effect of XFBD on Symptom Severity Score within 28 days of enrollment in the XFBD and placebo treatment.
- 1.3.2. To document the proportion of patients who are compliant taking greater than 90% of the test substance as measured by self-report
- 1.3.3. To document the proportion of patients who comply with symptom monitoring.
- 1.3.4. To document the proportion of patients who comply with repeated clinical testing.
- 1.3.5. To document the hospital-free days from enrollment to 42 days (number of days patient not in hospital).
- 1.3.6. To document cumulative incidence of serious adverse events, and adverse events leading to early discontinuation of XFBD or placebo.
- 1.3.7. To document cumulative incidence of grade 3 and 4 adverse events.
- 1.3.8. To obtain levels (detectable versus not detectable, and continuous on log10 scale) of SARS-CoV-2 RNA from nasal swabs at approximately days 1, 7 and 14 among a subset.

1.4. *Exploratory Objectives*

- 1.4.1. To document the rate of subjects tested as negative for SARS-CoV-2 at day 14.
- 1.4.2. To document the rate of housemate infection.
- 1.4.3. To document if XFBD changed the severity and duration of self-reported symptom experience of COVID-19.

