10.2.2 Secondary Outcome Measures

- 10.2.2.1 To document the effect of XFBD on Symptom Severity Score within 28 days of

study entry.

- 10.2.2.2 To document the proportion of patients who are compliant taking greater than 90% of the test substance as measured by self-report
- 10.2.2.3 To document the proportion of patients who comply with symptom monitoring.
- 10.2.2.4 To document the proportion of patients who comply with repeated clinical testing.
- 10.2.2.5 To document cumulative incidence of serious adverse events, and adverse events leading to early discontinuation of XFBD or placebo.
- 10.2.2.6 To document cumulative incidence of grade 3 and 4 adverse events.
- 10.2.2.7 To obtain levels (detectable versus not detectable, and continuous on log10 scale) of SARS-CoV-2 RNA from nasal swabs at approximately days 1, 7 and 14 among a subset.

10.3 *Randomization and Stratification*

[figure not shown]
Eligible participants will be randomized using a 1:1 ratio to each of the study arms. Housemates of participants previously enrolled will be independently randomized so that housemates will not be clustered within treatment group.

Randomization will be stratified by “high” vs “low” risk of severe disease, where “high” risk is defined by any of the following: age ≥ 60 years, or having any of a number of conditions, as described in section 3.3.

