10.6 Analyses

All descriptive statistics will be documented in total and stratified by age, race/ethnicity, gender, risk group and assigned treatment, when applicable. This pilot study is not powered to find statistically significant differences by treatment group.

All analyses involving randomized comparisons will include all randomized participants who received the first (**confirmed**) dose of study treatment, according to a modified intention-to-treat approach. However, as the study is blinded, the use of a modified intention-to-treat approach should not introduce bias into the comparison of randomized arms in this pilot study or in future larger-scale studies.

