10.6.2 Secondary Outcomes

Symptom severity scores will be determined from the COVID-19 symptom PROs reported daily by participants. Each symptom is rated by the participant on a scale from 0-4. Although the seriousness of the symptoms are not equal, summing the individual symptom ratings will give a rough measure of the participant's disease severity. These daily symptom severity scores will be summed over the 28-day period using area under the curve (AUC). Comparisons of this AUC, as well as weekly symptom severity scores, by age, race/ethnicity, gender, risk group and assigned treatment will be performed using Wilcoxon rank sum tests. For this, and all comparisons by demographic or treatment variables, the results will be considered for planning purposes only. Secondary outcomes 2, 3, and 4 involve compliance proportions and will be documented in total and compared by demographic and treatment variables using Fisher exact tests. Secondary outcomes 5, 6, and 7 involve event rates which will be calculated in total and compared by demographic and treatment variables using negative binomial regression. Detectable versus not detectable SARS-CoV-2 RNA from nasal swabs at days 7 and 14 will be compared by demographic and treatment variables using Fisher exact tests, and continuous measures of SARS-CoV-2 RNA (on log10 scale) will be assessed for normality and tested using t-tests or Wilcoxon rank sum tests, as appropriate.

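### Hospital-free days (1.3.5) counts days after death as hospital-free, and 10.2.2 and 10.6.2 leave its analysis unsettled

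*Combined protocol and SAP*

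**What the plan says.** Section 1.3 lists eight secondary objectives. The fifth, 1.3.5, reads "To document the hospital-free days from enrollment to 42 days (number of days patient not in hospital". No section adds that the patient must be alive, stops the count at death, or gives a death a score. Death in the same window is expected as an outcome, since primary objective 1.2.4 is "To document the rate of hospitalization or death within 42 days of enrollment in the XFBD and placebo treated groups".

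Section 10.2.2 lists seven secondary outcome measures, and hospital-free days is not among them. Its fifth item is "10.2.2.5 To document cumulative incidence of serious adverse events, and adverse events leading to early discontinuation of XFBD or placebo" and its seventh is "10.2.2.7 To obtain levels (detectable versus not detectable, and continuous on log10 scale) of SARS-CoV-2 RNA from nasal swabs".

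Section 10.6.2 never names hospital-free days. It gives outcomes 2 to 4 Fisher exact tests, and then says that outcomes "5, 6, and 7 involve event rates which will be calculated in total and compared by demographic and treatment variables using negative binomial regression". RNA follows with its own tests: "Detectable versus not detectable SARS-CoV-2 RNA from nasal swabs at days 7 and 14 will be compared by demographic and treatment variables" by Fisher exact tests, and the log10 level by t-test or Wilcoxon rank sum test. Of all comparisons by demographic or treatment variables, 10.6.2 says that "the results will be considered for planning purposes only". Section 10.6 adds a general provision: "All descriptive statistics will be documented in total and stratified by age, race/ethnicity, gender, risk group and assigned treatment, when applicable".

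**The concern.** A patient who has died is not in hospital, so the stated rule credits every day after death as hospital-free. An outcome meant to reward a good course then rewards an early death with little hospital use. An arm looks better if a survivor's admission is exchanged for a death that used fewer hospital days.

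Other outcomes do not repair this ranking. The composite in 1.2.4 counts a fatal and a survived admission alike, and 7.1 places COVID-19 deaths outside the adverse event and serious adverse event definitions.

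The gap in 10.2.2 matters for a second reason. Section 10.2 says that the measures listed there will be carried into the analysis plan of the later studies. As the text stands, hospital-free days either drops out of that list or is carried forward with the death rule unstated and the method unclear.

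**Working it through.** **Scoring.** The documents give no mean, standard deviation, length of stay or death rate for this outcome, so there is no planned figure to reproduce. The cases below are illustrative.

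Inputs: a 42-day window (1.3.5) and 30 participants per arm (section 3). Let H be the hospital days in a fatal course and S the stay of a survivor.

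- Score as written = 42 − hospital days, whatever the vital status.
- Fatal courses with H = 0, 3, 10, 20 score 42, 39, 32, 22.
- Survivors with S = 5, 10, 14 score 37, 32, 28.
- A death outscores a survivor if and only if H < S.
- The shift in the arm mean when one survivor is exchanged for one death is (S − H)/30.

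| Survivor's stay S | H = 0 | H = 3 | H = 10 | H = 20 |
|---|---|---|---|---|
| 5 days | +0.17 | +0.07 | −0.17 | −0.50 |
| 10 days | +0.33 | +0.23 | 0 | −0.33 |
| 14 days | +0.47 | +0.37 | +0.13 | −0.20 |

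For scale, take the event rates of 0.20 and 0.10 in 10.4. Assume that every event is an admission with a mean stay of 5, 10 or 14 days. The expected arm difference is then (0.20 − 0.10) × stay = 0.5, 1.0 or 1.4 days. At 10-day stays, one exchange worth 0.23 day is about a quarter of that difference.

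**Would an alive condition be enough?** Days alive and out of hospital = day of death − H for a death, and 42 − S for a survivor. A death at home on day 33 without admission scores 33 − 0 = 33, against 42 − 10 = 32 for a 10-day survivor. A death at home on day 40 scores 40, against 42 − 7 = 35 for a 7-day survivor. Late deaths at home can still outrank survivors, so death needs a stated rank.

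**Numbering.** Items 1 to 4 agree in the two lists. After that they diverge:

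| Item | List 1.3 | List 10.2.2 |
|---|---|---|
| 5 | Hospital-free days | Serious AEs and AEs leading to discontinuation |
| 6 | Serious AEs and AEs leading to discontinuation | Grade 3 and 4 AEs |
| 7 | Grade 3 and 4 AEs | RNA levels |
| 8 | RNA levels | (none) |

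- Under the 1.3 numbering, hospital-free days falls among outcomes 5 to 7 and gets negative binomial regression as an event rate. RNA is item 8 and has only its separate tests. The text does not say whether the response would be the score capped at 42 or hospital days over person-time.
- Under the 10.2.2 numbering, hospital-free days has no named comparative test, only the descriptive summary by arm in 10.6. RNA would get negative binomial regression as well as its own tests.

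The 1.3 numbering fits the text of 10.6.2 better, but 10.2.2 is the list within the statistical section. The documents do not settle which is meant.

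**The case against.** The strongest reply is that the misranking may never occur. It needs a death by day 42 with fewer hospital days than some survivor's stay. Entry excludes severe and critical disease (4.3.2), people over 75 (4.2.2) and, unless waived, those meeting the emergency-use high-risk criteria (4.3.14). The documents give no mortality figure. At an assumed 42-day mortality of 0.5%, 1% or 2%, the chance of no death among 60 is 0.995^60 = 74%, 0.99^60 = 55% or 0.98^60 = 30%. This stands and limits the weight of the point, but it does not make the rule right.

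Nor is death hidden. It is part of a primary outcome, 9.2 has sites seek vital status and date of death after early discontinuation, and any death among 60 people would be individually visible. This stands too, although the ranking within 1.3.5 stays wrong.

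It can also be argued that days alive and out of hospital, with deaths reported alongside, is an acceptable definition. It does remove the days after death. It still leaves the late death at home above a survivor with a longer stay.

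On method, a reader might infer that negative binomial regression is safely conservative here, or that the Wilcoxon test would recover much lost information. Neither is supported. In simulations with assumed lengths of stay and no deaths, negative binomial regression on hospital days rejected a true null in 1.2 to 3.3% of runs at 15% admission in both arms, but in 4.9 to 6.9% at 10%. At 20% against 10%, the Wilcoxon test and a chi-square test of any admission both had power of about 17 to 20%. With no deaths simulated, these runs say nothing about how death is scored.

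**Conclusion.** The point holds as a modest but real defect that should be fixed. The stated rule counts days after death as hospital-free, and nothing elsewhere corrects it. The omission from 10.2.2 and the assignment of methods by number leave the analysis ambiguous. In the illustrative cases, the exchanges that favor the arm with the death move its mean by 0.07 to 0.47 day each. These sizes rest on assumed hospital days, because the documents supply none. The investigators may have intended an alive condition, but the text does not state one.

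A reader might infer that every death scores better than a survivor. That is not so: a fatal course with 20 hospital days scores 22, below all three survivors in the working. A reader might also infer that the trial's mortality or primary results are compromised. The documents do not support that either. Death by day 42 is counted in 1.2.4, the outcome at issue is secondary, comparisons serve planning only, and 10.6 already says the pilot is not powered for treatment differences.

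**What to change.** - **1.3.5:** define the outcome as days alive and out of hospital from enrollment through Day 42, with death by Day 42 ranked worst, below a survivor who was in hospital throughout.
- **10.2.2:** add the outcome to the list.
- **10.6.2:** refer to each outcome by name instead of number. Compare arms on hospital-free days with the Wilcoxon rank sum test already used in that section, because the score is bounded and piles up at 42 and is not an event rate. Negative binomial regression can stay for the adverse-event outcomes.
- **Reporting:** show deaths and hospital days by arm beside the score. Use the worst-rank value only for ranking, and do not average it as if it were days.

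The cost is wording in three places and a check that the eCRF captures admission, discharge and death dates. The Day 42 record review (6.2.15) and the vital-status follow-up in 9.2 make this feasible, but the documents do not name all of these fields. The ranked composite is slightly harder to interpret. With most participants tied at 42, the Wilcoxon test will add little beyond a test of any admission.

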2. INTRODUCTION

2.1. Background Threat

A novel pneumonia caused by a previously unknown betacoronavirus emerged in Wuhan, China, in December 2019. The virus is closely related to the severe acute respiratory syndrome coronavirus (SARS CoV), which led to an outbreak in 2003 causing the disease SARS, and has been named SARS-CoV-2. The human disease caused by SARS-CoV-2 is called COVID-19.

During the current SARS-CoV-2 outbreak, the incidence of known cases has rapidly increased such that, on January 5, 2020, there were 59 confirmed cases, 278 cases on January 20, 2118 cases on January 26, and more than 80,000 cases and 2700 deaths by February 25, 2020, according to various international health reporting agencies. As a result, on January 30, 2020, the International Health Regulations Emergency Committee of the World Health Organization (WHO) declared the COVID-19 outbreak a Public Health Emergency of International Concern. On January 31, 2020, the US Department of Health and Human Services declared a public health emergency in the United States. As of July 14, 2020, there are more than 13 million cases of COVID-19 globally, including over 3.3 million cases in the United States (US), resulting in a total of over 574,000 deaths globally, with over 136,000 deaths in the US. Despite quarantine measures, SARS-CoV-2 continues to spread (1). Outbreak forecasting and modeling suggest that these numbers will continue to rise (2).

Global efforts to evaluate novel antivirals and therapeutic interventions to treat COVID-19 have intensified. There is currently no approved therapeutic agent to treat COVID-19 effectively. Therefore, there is an urgent public health need for the rapid development of novel interventions.

Virology

Coronaviruses (CoVs) are positive-sense, single stranded, enveloped RNA viruses, many of which are commonly found in humans and cause mild symptoms. Over the past two decades, emerging pathogenic CoVs capable of causing life-threatening disease in humans and animals have been identified, namely, SARS-CoV-1 in 2002-2003 and Middle East Respiratory Syndrome coronavirus (MERS-CoV) in 2012.

Disease Course

Once infection occurs, the clinical course is variable. Best current data suggests that fewer than 2.5% of infected persons will show symptoms within 2.2 days (CI, 1.8 to 2.9 days) of exposure, and symptom onset will occur within 11.5 days (CI, 8.2 to 15.6 days) for 97.5% of infected persons" (3) In most (~80%) cases, COVID-19 presents as a mild-to-moderately severe, self-limited acute respiratory illness with fever, cough, and shortness of breath. It remains unclear exactly what the rate of progression of COVID-19 is and what the predictors are for complications, including pneumonia, acute respiratory distress syndrome (ARDS), kidney failure, and death. It is also clear that older age, male sex, and comorbidities, including diabetes and hypertension, increase the risk for worse outcomes (Figure 2.1-1) (4-6). In a recent meta-analysis, the main clinical symptoms were fever (88.5%), cough (68.6%), myalgia or fatigue (35.8%), expectoration (28.2%), and dyspnea (21.9%). Minor symptoms included headache or dizziness (12.1%), diarrhea (4.8%), and nausea and vomiting (3.9%). Laboratory examinations showed that lymphocytopenia (64.5%), increase of C-reactive protein (CRP) (44.3%), increase of lactate dehydrogenase (LDH) (28.3%), and leukocytopenia (29.4%) were more common in those with COVID-19 (7).

[figure not shown]

Figure 2.1: Timeline of COVID Disease Progression after Hospitalization.

Onset refers to onset of symptoms.

Viral infections jump from host to host through a variety of pathways. CoVs do this through respiratory droplets. Understanding this shedding is important to understanding epidemic spread and how shedding relates to disease progression. The best evidence available now suggests that viral shedding, especially in upper respiratory secretions, is detectable around 2 days before symptoms develop in people and continues throughout the symptomatic phase. This shedding can be quite high during active disease and can continue for up to 37 days, with a quarter of persons still shedding at 3 weeks, as detected by nasopharyngeal swabs (4).

Biomedical Interventions

There are no approved treatments for COVID-19. Some agents have shown activity against other betacoronaviruses, such as lopinavir/ritonavir, chlorpromazine, nitazoxanide, gemcitabine, and dasatinib (9), and two agents have shown *in vitro* activity against the virus, including chloroquine and the adenosine analog remdesivir (10). There is no clinically proven antiviral treatment for SARS-CoV-2 infection, although a clinical trial of remdesivir (11) is underway in China and the US for severe pulmonary disease (12), and anecdotal evidence has been published about Hydroxychloroquine and Azithro (13).

TCM Interventions

From February 16th to 24th, the Huazhong University of Science and Technology team completed 9 autopsies of patients treated with non-invasive ventilation and died from COVID-19. The preprints are available. (14)

The autopsy reports showed that a gray-white viscous liquid appeared in the lung tissue samples, a white foamy mucus was found in the trachea, and a sticky jelly-like mucus was found in the bronchi of the right lung as well as significant and severe fibrinoid exudate in alveolar spaces. The authors suggest that COVID-19 pneumonia mainly results from inflammatory reactions characterized by deep airway and alveolar damage.

With this thick mucus occupying the alveoli, bronchi and pulmonary interstitium, respiratory function is significantly reduced. As a result, the patient's blood oxygen saturation can be reduced to 80% or lower. In comparison to the 95% and above oxygen saturation of healthy individuals, the patient is considered hypoxic.

Patients with hypoxia can be put on oxygen therapy to improve their oxygen saturation. However, if the patient's lungs are unable to complete the oxygen exchange, no amount of concentrated oxygen will improve their blood oxygen saturation. Unlike SARS patients with hyaline membranes in the alveoli, COVID-19 patients had mucous plugs in all the respiratory tracts, terminal bronchioles, and pulmonary alveoli. These mucus plugs in the distal respiratory tracts seemed to have played a part in the failure of sputum suction by bronchoscopy. (15)

After the autopsies, nearly 10,000 patients in *fangcang* (mobile cabin) hospitals specifically built for the COVID-19 outbreaks utilized traditional Chinese medicine with a coverage of 95% of all *fangcang* patients.

According to Chinese national statistics, 91.5% of confirmed diagnosed patients (74,187) were prescribed TCM. There were those who refused or were found unsuitable to use TCM. Hubei province alone accounted for 61,449 (90.6%) of patients who utilized TCM. Clinical observation showed that 90% of mild and moderate cases were successfully relieved of their symptoms and/or prevented progression into severe and critical condition. (16)

Currently, in Wuhan, the hospitalized patients with COVID-19 went from 60,000 two months ago to approximately 5000, and patients with severe illness decreased from 12,000 to approximately 1800. They had a period of 5 days without any increased new cases, critical cases, or deaths. (17)

TCM Background

Traditional Chinese medicine (TCM) takes a holistic approach in treating disease and categorizes health disorders from both its origin and the resulting symptoms. The origin of an illness can be from either cold or heat; the resulting symptoms can be cold-based (i.e. shivering, watery diarrhea, edema, cough with profuse, thin, and clear phlegm, etc.) or heat-based (i.e. fever, dry cough, sore throat, cough with thick, yellow phlegm, dysentery, etc.) The basis of treatment is to eliminate the original cause while treating the resulting symptoms concurrently.

Given the autopsy results and clinical presentation, in TCM theory, SARS-CoV-2 is seen as thriving in cold and damp weather while the disease COVID-19 consists of mostly warm-heat symptoms (i.e. fever, dry cough, heat induced cough with yellow phlegm). The TCM medicinals used in the treatment of COVID-19 mainly consist of heat-clearing and toxin-removing medicinals to reduce fever and clear away bacteria and viruses; cough-suppressing and phlegm-transforming medicinals to thin the phlegm so it is easier to expectorate; and lung-diffusing and pant-calming to soothe the tracheal smooth muscle and relieve symptoms of dyspnea.

The prescriptions for the prevention and treatment of COVID-19 were selected *Shang Han Lun*, or Treatise on Cold Damage Disorders, dated to the end of the Han Dynasty (220 AD). (18) In this treatise, all the diseases originate from cold, but the symptoms could either be cold-based or heat-based. This ancient treatise is a well-known reference for traditional Chinese medicine practitioners. Some of the botanical medicinals in the chosen prescriptions have also been isolated and developed into conventional medicine. (19)

For example, ephedrine can be isolated and extracted from *ephedrae herba* (麻黃 *mahuang*). Ephedrine is a stimulant that excites the sympathetic nervous system, constricting blood vessels to act as a pressor and bronchodilator. In traditional Chinese medicine, the function of *ephedrae herba* is recognized similarly and is mostly used to treat bronchial asthma and prevent asthma attacks. (20-22)

Another example is *Glycyrrhizae radix et rhizoma* (甘草 *gancao*), also known as Chinese liquorice, which is a medicinal and can also be used as a sweetener in food products. The medicinal function includes clearing heat (including the reduction of fever), removing toxins (anti-infection, anti-infective), loosening and transforming phlegm to eliminate, suppressing cough, easing tension, and relieving pain. This medicinal is used in the treatment of sore throat, oral mucosa ulcers, cough, palpitations, and pain.

Generally, the design of a TCM prescription takes into account the source of the illness, the resulting symptoms, the external environment, and the personal constitution of the patient. In the following delineation, this document focuses on the aspects of a broad application TCM in which the prescription is balanced to be less dependent on environmental and individual factors for general application.

Potential Risks of XFBD

XFBD contains *ephedra herba*, which has levels of ephedrine and pseudoephedrine. Both are known sympathomimetic agents, which can cause an increase in blood pressure and heart rate. The level of ephedrine and pseudoephedrine in each packet is at most 15mg or 30mg per day. In some over-the-counter (OTC) medication, the daily dose of pseudoephedrine can exceed 300 mg, which is 10 times the daily dosage of ephedrine and pseudoephedrine in XFBD.

armeniaceae semen amarum with levels of amygdalin, or laetile. In TCM prescription theory and analysis, the levels of amygdalin are lower in the XFBD combination than in the plant *armeniaceae semen amarum* alone. The level of *armeniaceae semen amarum* in each packet is at most 80mg per day. Various studies have shown that 80mg is well below the level of toxicities manifesting.

Assessment of Potential Risks and Benefits

There is human clinical data on the XFBD prescription in Wuhan, China, with over 280 patients in clinical trials and approximately 6,000 patients in clinical care. In Wuhan, China, they saw a 50% reduction in progression of disease for patients with mild or moderate COVID-19 disease. (personal correspondence with [name] [name], dated Mar 31, 2020) The small risk with the use of the granules, including 30 mg of ephedrine per day, is amply outweighed by the potential for reducing serious consequences COVID-19 progression.

2.2. *Rationale*

At present, there is no specific antiviral therapy for COVID-19. Few treatment studies have been conducted because most human CoV strains cause self-limited disease, and care is supportive. After SARS-CoV-1 was identified in 2002-2003 and caused a large global outbreak, there was an increased interest in the development of specific therapeutic agents. SARS-CoV-1 patients were treated with corticosteroids, type 1 IFN agents, convalescent plasma, ribavirin, and lopinavir or ritonavir; except for

ribavirin, many of these agents have in vitro pre-clinical data that support their efficacy (42-57).

Given the lack of specific antiviral therapy for SARS-CoV-2 infection, and the known XFBD formulation, based on pre-clinical and small clinical studies, this randomized, placebo-controlled trial will evaluate the efficacy and safety of XFBD formulation in persons who have active SARS-CoV-2 infection and mild to moderate COVID-19 symptoms.

Why XFBD for COVID-19?

Xuanfei Baidu granules (XFBD) were developed by [name], a member of the Chinese Academy of Engineering, and his team. They used this on the frontline in Hubei, Wuhan, under the direction of [name] and [name], Director of the Capital Medical University Beijing Hospital of Traditional Chinese Medicine.

Expert Recommendation on Usage: Suitable for mild, moderate, and severe cases. For critical cases, at doctor's discretion, based on the patient's condition.

Typically, in China, TCM prescriptions need to be boiled into a decoction and taken orally. For convenience, this TCM medicinal for COVID-19 control has been manufactured as a drink mix at the Tianjin Tasly Pharmaceutical Co., LTD (<https://www.tasly.com>), a well-established and leading TCM research and manufacture center to integrate technology and innovation to update the practice of TCM for human health.

The granules are already packaged into 10g packet per dose, 2 packets per day. These TCM packets have passed quality control tests for potency and standardization. To be taken in the morning and evening mixed into hot water to be taken 1 hour after a meal and 1 hour before or after conventional medicines:

Chinese	Latin	Amount (g) of crude medicinal for 1000g of final XFBD product	Source
麻黃 (A,B)	Ephedrae Herba	150	Ephedra sinica Stapf
苦杏仁 (A,B)	Armeniacae Semen Amarum	375	Prunus sibirica L.
生石膏 (A,B)	Gypsum Fibrosum	750	$\text{CaSO}_4 \cdot 2\text{H}_2\text{O}$
薏苡仁 (B,C)	Coicis Semen	750	Coix Lacryma-jobi L.yar.mayuen
苍术 (G)	Atractylodis Rhizoma	250	Atractylodes chinensis (DC.) Koidz.
广藿香 (G)	Pogostemonis Herba	375	Pogostemon cabLin (Blanco) Benth.
青蒿 (H)	Artemisiae Annuae Herba	300	Artemisia annua L.
马鞭草 (E)	Verbena Herba	500	Verbena Officinalis L.
虎杖 (F)	Polygoni Cuspidati Rhizoma et Radix	750	Polygonum cuspidatum Sieb.et Zucc.
芦根 (C)	Phragmitis Rhizoma	750	Phragmites communis Trin.
葶苈子 (D)	Descurainiae Semen	375	Descurainia sophia (L.) Webb. ex Prantl.
化橘红 (H)	Citri Grandis Exocarpium	375	Citrus grandis (L.) Osbeck
甘草 (A,B)	Glycyrrhizae Radix et Rhizoma	250	Glycyrrhiza uralensis Fisch.

This prescription was derived from **four** previous prescriptions that have been in routine use in TCM over centuries and have been shown to be safe.

A. 麻杏石甘汤 Maxing Shigan Tang (麻黃 Ephedrae Herba, 苦杏仁 Armeniacae Semen Amarum, 石膏 Gypsum Fibrosum, 甘草 Glycyrrhizae Radix et Rhizoma) is a traditional preparation recorded from Shang Han Lun used to diffuse the lungs, calm panting, and clear heat. (23) The traditional

idea is cough and shortness of breath come from the lungs being congested or “unable to allow normal qi movement of the lungs.” (24) The ephedrae herba and gypsum fibrosum are a known pair to reduce fever and diffuse the lungs. (25) Ephedrae herba has been banned by the FDA in dietary supplements; however, the usage in TCM has not been restricted. (26) The concern stemmed from the various overdoses of epinephrine found in the plant *Ephedra sinica* Stapf in which the dried aerial parts are used in TCM. It has been found that the amounts of epinephrine and norepinephrine detected in the decoction of *maxing shigan tang* was much lower than in ephedrae herba alone. (27) Another common concern is the amount of amygdalin present in armeniacae semen amarum as it can be toxic in large amounts. There are a couple of studies showing that the concurrent usage of gypsum fibrosum and glycyrrhizae radix et rhizoma can decrease the amount of amygdalin content found in the prescription. (28-29) The studies showed that by combining the use of gypsum fibrosum and glycyrrhizae radix et rhizoma, the total levels of amygdalin are, in fact, lower than the levels if armeniacae semen amarum were used alone. These reports support the theory of TCM prescribing which uses specific combinations of medicinals to decrease toxicity and enhance efficacy. Rather than having direct bearing on acceptable amygdalin levels, these reports are intended to reinforce the efforts to mitigate toxicities and to show that the toxicity of using armeniacae semen amarum on its own is higher than that used in combination.

B. 麻杏薏甘汤 Maxing Yigan Tang (麻黃 Ephedrae Herba, 苦杏仁 Armeniacae Semen Amarum, 薏仁 Coicis Semen, 甘草 Glycyrrhizae Radix et Rhizoma) is a variation of the prescription above with coicis semen instead of gypsum fibrosum. Coicis semen, also colloquially known as Job’s tears, is used to disinhibit water and drain dampness (such as reducing edema), strengthen the spleen and stop loose stools, and resolve toxins and dissipate congestion. This medicinal is also a common food item in cereals, teas, and even distilled liquors.

C. 千金苇金汤 Qianjin Weijing Tang (芦根 Phragmitis Rhizoma, 薏仁 Coicis Semen, etc.) is a prescription used to transforms phlegm and clears the lungs. This prescription has been used in randomized controlled trials on its own or in combination with other prescriptions for the treatment of bronchiectasis, asthma, and community-acquired pneumonia. (30-31)

D. 荸荔大枣泻肺汤 Tinglidaozao Xiefei Tang (荸荔子 Descurainiae Semen / Lepidii Semen, etc.) is a prescription used to drain the lungs, reduce inflammation, disinhibit water, and calm panting. Descurainiae Semen / Lepidii Semen is commonly used in combination with glycyrrhizae radix et rhizoma and armeniacae semen amarum to treat symptoms of cough and shortness of breath. (32) This prescription, combined with maxing shigan tang as described above, also showed positive results in a small randomized controlled trial for elderly patients with community-acquired pneumonia. (33)

Other consideration to developing the prescription, additional medicinals:

E. Antibacterial and Antiviral Activity: 马鞭草 Verbena Herba contains compounds that have shown to be inhibitory towards bacteria (such as gram-negative *E.coli* and gram-positive *Staphylococcus aureus*) and viruses such as hepatitis B virus (HBV). (34) This medicinal has a low toxicity profile but should not be used in pregnant patients. (35-36)

F. Microvascular Thrombosis: From the autopsy, patients had significant micro-clotting, or microvascular thrombosis. 虎杖 *Polygoni cuspidi* rhizoma et radix can help clear heat (such as reduce fever), suppress cough, transform phlegm, and dissipate stasis (such as dissolving blood clots). [personal correspondence with [name] [name] dated March 31, 2020] Verbena herba also has blood quickening and stasis dissipating actions that could help break up the micro-clots without having a full anticoagulating effect. (34)

G. Gastrointestinal: Both 薏香 *Pogostemonis* Herba and 苍术 *Atractylodis* Rhizoma help with gastrointestinal discomfort. *Pogostemonis* herba harmonizes the stomach (such as helping nausea, bloating, gastroprotective effects, etc.) and disperses damp. (37-38)

- H.* Transforming Phlegm: 化橘红 *Citri grandis* exocarpium can help the phlegm to resolve mucus plugs in the lungs. (39) This is dried pomelo peel, which can be found in foods such as teas and candies.
- I.* Clearing heat: 青蒿 *Artemisiae Annuae Herba* is better known as the source of artemisinin used for malaria. In TCM, *artemisiae annuae herba* is described mainly as an antimalarial agent but also a heat-clearing agent. The component artemisinin has varying degrees of anti-inflammatory and antiviral effects for DNA and RNA viruses. (40) It may also help regulate the immune system, such as reducing the release of proinflammatory cytokines. (41)

Wuhan Experience: Wuhan Jiangxia *Fangcang* Hospital used TCM prescriptions and other traditional methods (such as acupuncture, guasha, medicinal patches, etc.) in the treatment of COVID-19 while continuing the patient's previous conventional medicines for underlying health conditions. From February 14th to March 10th, the hospital treated a total of 564 patients with mild (71%) and moderate (29%) COVID-19. Upon hospitalization, approximately 30% of the patients had symptoms of fatigue and shortness of breath, while another approximately 40% had cough. Within the 14-day treatment and subsequent observation period, 482 patients recovered and were discharged. Among the patients admitted, none of their conditions progressed to severe or critical. It is of note that at Wuhan Jiangxia *Fangcang* Hospital, two main prescriptions with the addition of other TCM treatment modalities were used. The medical staff was also free of infection [personal correspondence with [name] [name] dated March 31, 2020]

For the *Xuanfei Baidu* prescription, which was given to 273 patients, none of them progressed to severe or critical condition. 250 patients achieved two consecutive negative viral RNA tests in which the average time frame was about 11.02 ± 3.59 days, with a 95% confidence interval (CI). 230 patients saw a significant improvement in their CT scans in about 13.13 ± 4.20 days with a CI 95%. [personal correspondence with [name], dated April 28, 2020]

At another *fangcang* hospital which had 330 patients, TCM was not used or if used, in an unstandardized manner, and 32 patients (9.7%) of those patients progressed to severe or critical condition. Other *fangcang* hospitals that utilized TCM prescriptions also saw a decrease in patients' progression of disease to approximately 2-5%. [personal correspondence with [name] [name] dated March 31, 2020]

